11.1. Data collection procedure

During HCP catheterisations at visit 1 and 2 a catheterisation profile is created using a scale connected to a data box. The catheterisation profile shows a scale curve of accumulated urine (urine volume/time). The catheterisation profiles are analysed by two Coloplast specialists, independently, and results then compared to derive the relevant endpoints. The data for the catheterisation profile relevant endpoints are then uploaded to the database by the data management specialist.

Discomfort will be assessed using the visual analog scale (VAS). The subject will be asked to indicate the level of discomfort (from 'No discomfort' and 'Worst possible discomfort') in a 10 cm line on paper. Hereafter, the site personnel must measure the length (cm) from the start of the line to the subject's mark and add to the paper form. In addition, the site personnel must register the number in the eCRF.

The remaining endpoints, assessment, backup measurements and baseline information can be entered directly into the eCRF.

At the end of the study a formal data review meeting will be performed before the database will be locked.

The Data Management procedures are further described in the Data Management instructions.

The principal investigator will keep a separate list of the subjects' ID numbers, names, and addresses in a locked room/cabinet. Only data referred to in this clinical investigation plan will be recorded in the CRFs.

Adverse events should be registered following the timelines described in the Adverse Event section.

11.2. Data retention

The Investigator file must be archived for a minimum period of 10 years after the final clinical investigation report has been signed.

12. Amendments to the Clinical Investigation Plan

No changes in the clinical investigation procedures shall be affected without mutual agreement between the principal investigator and the sponsor. The agreement of the changes must be documented by signing the corresponding clinical investigation plan amendments and registered in the Change Log.

All significant changes require notification to the EC and applicable regulatory authority. Substantial changes may require approval from the EC and applicable regulatory authority prior to implementation.

13. Deviations from the Clinical Investigation Plan

Deviations to the Clinical Investigation Plan occurs when the activities during the clinical investigation do not comply with the EC and CA approved investigation plan.

A minor deviation is defined as those that don't increase risk or decrease benefit or don't have a significant effect on the subject's rights, safety or welfare; and/or on the integrity of the data. If a deviation increases risk or decreases benefit and/or has a significant effect on the subject's rights, safety or welfare and/or has a significant effect on the integrity of the data it is defined as a major deviation and the Investigator must inform the monitor immediately, and the Monitor will report and inform the Clinical Manager or designee immediately.

The investigator is not allowed to deviate from the Clinical Investigation Plan unless, under emergency circumstances or to protect the rights, safety and welfare of the subject(s).

For the purposes of this investigation, any variance from the protocol is considered a deviation and is to be reported.

The site will complete a deviation eCRF form for all data-related deviations and all deviations that are not related to the data (for example, an untrained nurse performing study procedures) are reported by the monitor in the Site Report – Periodic Monitoring and actions are addressed to the Investigator for completion.

If any deviations to the investigation plan are detected during the monitoring visit, the Monitor shall ensure the site reports all deviations in the eCRF or on the Deviation log in the Investigator File. Additionally, the monitor must report any deviation noted during the visit in the Periodic Monitoring Report.

Monitor will align with data management in each investigation, how data management will be informed about all deviations.

The following information about the deviation will be collected:

- Site ID
- Subject ID
- Date the deviation took place
- What the deviation is related to
- If the deviation affects data integrity
- If the deviation affects subject safety
- Supplementary description of the deviation
- Actions taken with regards to the deviation

14. Device Accountability

All access to the investigational devices (including comparators) used in the clinical investigation is controlled by storage procedures and device accountability logs as described below. The investigational devices must only be used in this clinical investigation and only according to the CIP.

Sponsor keeps a device accountability log that states the physical location of all investigational devices from shipment of investigations devices to the investigational sites until return of or disposal.

The PI or an authorized designee keeps records documenting the receipt, use and return and disposal of the investigational devices, which includes:

- Date of receipt.
- Identification of each investigational device (batch no./serial no./unique code).
- The expire date.
- The date(s) of use.
- Subject identification.
 - The date on which the investigational device was returned/explanted from the subject
 - The date of return unused, expired or malfunctioning investigational devices

15. Statement of compliance

The clinical investigation is conducted in accordance with:

- Ethical principles that have their origin in the Declaration of Helsinki, 1964, Last amended at the 59th WMA General Assembly, Brazil, October 2013.
- MDR (EU) 2017/745
- ISO 14155:2020 "Clinical Investigation of medical devices for human subjects – Good clinical practices".
- Any applicable regional or national regulations will be specified in the country specific CIP.

15.1. Ethics committee and regulatory authorities

The CIP and/or other relevant documents are submitted to the appropriate EC(s) and regulatory authorities. This clinical investigation will not begin until the required approval from the EC and regulatory authorities have been obtained. Any amendment to the protocol will be submitted to the same EC(s) and regulatory authority.

Sponsor will notify the relevant regulatory authority and EC(s) concerned of the end of the clinical investigation.

15.2. Data protection

As part of the investigation Coloplast A/S, [name] ("Coloplast") will collect and process the personal information the subject provides for the investigation ("subject personal data"). This includes identification and contact information (which may be anonymised depending on the nature of the investigation) as well as information about product usage experience and your health. Coloplast will comply with the EU General Data Protection Regulation (GDPR) and the Danish act on data protection ("databeskyttelsesloven"), including in connection with transfer of data to third countries, cf. chapter V of GDPR, Coloplast will only process the subjects' personal data:

1. To conduct the investigation and carry out related research based on subject consent (primary use), cf. articles 6(1)(a) and 9(2)(a) of GDPR,
2. To comply with applicable legal obligations to e.g. ensure reliability and safety, cf. article 6(1)l in conjunction with article 9(1)(i) of GDPR, and
3. If separate consent is given for secondary use of subject personal data, cf. articles 6(1)(a) and 9(2)(a) of GDPR – carry out research outside the clinical protocol to improve Coloplast's products and services, and for use in education.

Part of Coloplast's processing is carried out on third-party platforms (clinical trial databases) and certain third parties are assisting Coloplast in the processing (e.g. the investigator). Such cases will imply a transfer of your

personal data to the third parties, but solely for the specified purposes and with the third parties acting on instruction from Coloplast. Data may be collected and processed across the Coloplast network, which may entail processing of personal data outside the European Economic Area. In such cases, an adequate level of protection will be ensured by the third parties being subject to the standard contractual clauses on data protection adopted by the EU or to an EU-approved certification mechanism on data protection. For further information about this please the subject can always consult Coloplast's data protection officer (details below).

Subject personal data will be kept as long as required under applicable laws and regulations. The EU Medical Device Regulation obligates Coloplast to keep the data for a period of at least ten years after the investigation is completed, or, in the event that the device is subsequently placed on the market, at least ten years after the last device has been placed on the market. Subject personal data will be deleted at the end of the mandatory retention period.

If the subject has questions or queries regarding Coloplast's handling of personal information, the subject can always contact Coloplast's Data Protection Officer at [REDACTED] Complaints related to Coloplast's handling of subject personal information may similarly be sent to the Data Protection Officer, and the subject is also entitled to file a complaint with the relevant supervisory authority, which in the case of Denmark is the Danish Data Protection Agency (www.datatilsynet.dk).

The subject can write to [REDACTED] at any time to request:

- Access to personal data
- Correction of errors in personal data or to erase personal data
- Limit what can be done with personal data
- To receive personal data in machine-readable format (data portability).
- Withdrawal of consents the subject has given Coloplast to process personal data

15.3. Indemnity

All subjects are fully covered by Coloplast A/S insurance throughout the investigation.

15.4. Financial conditions

Coloplast A/S will compensate all investigators involved in the clinical investigation for their time and resources spent on the investigation. All financial agreements with the investigation sites involved in the clinical investigation will be specified in a sponsor investigator agreement.

16. Informed consent process

Written informed consent is obtained from all subjects participating in the investigation after thorough written and verbal information. The information is given by the investigator or his/her representative in the subjects' native non-technical language. Each subject will be fully informed about the aim of the investigation, procedures, potential risks or inconveniences and/or expected benefits, *all anticipated adverse device effects* and then have a minimum of *24h (ensure ample time)* before deciding on participation. The subjects will be informed that their participation is voluntary and that they may leave the investigation at any time, without this having any influence on their further treatment.

The informed consent signature form includes personally dated signatures of the subject and the PI or his/her representative responsible for conducting the informed consent process. A copy will be provided to the subject.

If new information is to be given during the investigation, sponsor will inform the investigators, and the new information is given to the subjects by the investigator. If new information becomes available that can significantly affect a subject's future health and medical care that information will be provided to the subject in

written form. CM is responsible for writing the information and providing the approved Subject Information and Consent Form to investigators that will further provide it to the subjects. If applicable, all affected subjects shall be asked to confirm their continuing informed consent in writing.

This procedure also applies to informed consent obtained from a subject's legal representative. The procedure cannot waive the subjects' legal rights.

17. Subject compensation

17.1. Compensation in case of injury

Product liability and No-Fault Clinical Investigation Insurance covering the duration of the clinical investigation are in place, to enable compensation in the event of an injury to a participating subject.

17.2. Compensation for participating in the clinical investigation

This is to compensate for any inconvenience caused during the conduct of the study catheterisations and time used. Travel expenses will be accounted for separately. For Danish subjects, the remuneration/vouchers are taxable (B-income) and it is the responsibility of the subject to declare this to SKAT.

18. Adverse events, adverse device effects and device deficiencies

18.1. Adverse events

An adverse event is any untoward medical occurrence, unintended disease or injury, or untoward clinical signs (including abnormal laboratory findings) in subjects, whether or not related to the investigational medical device(s) or the comparator(s), or the procedures involved. The adverse event shall be marked with the intensity mild, moderate or severe. This could include events such as headache or dizziness.

18.2. Adverse device effect

An adverse event, which is related to the use of the investigational medical device (including comparator), is an adverse device effect, and should be marked as unlikely related, possible related, probable related or with causal relationship on the adverse event form.

The definition of an adverse device effect includes any event resulting from insufficiencies or inadequacies in the instruction for use, *deployment*, or any malfunction of the medical device, as well as any event resulting from use error or from intentional misuse of the device.

Table 1 lists anticipated adverse device effects that may occur.

Table 1 Anticipated adverse device effects and their likely incidence rates

ANTICIPATED ADE	INCIDENCE RATE
Irritation of mucosa	Likely
Stinging and pain in urethra during catheterisation	Likely
Macroscopic haematuria	Unlikely
Macroscopic leukocytes	Unlikely
Urinary tract infection	Very unlikely

18.3. Device deficiency

A device deficiency is the inadequacy of the investigational medical device or comparator with respect to its identity, quality, durability, reliability, usability, safety or performance. This includes malfunctions, use errors and inadequacy in the information supplied by the manufacturer including labelling.

EXAMPLES OF DEVICE DEFICIENCY

No coating on investigational device

No micro-holes

Broken packaging

Broken catheter

18.4. Serious adverse events (SAE)

A serious adverse event is an adverse event that:

- Led to death,
- Led to a serious deterioration in the health of the subject, users or other persons as defined by one or more of the following:
 - 1) a life-threatening illness or injury, or
 - 2) a permanent impairment of a body structure or a body function including chronic diseases, or
 - 3) in-patient or prolonged hospitalization, or
 - 4) medical or surgical intervention to prevent life-threatening illness or injury or permanent impairment to a body structure or a body function.
- Led to foetal distress, foetal death, a congenital abnormality or birth defect including physical or mental impairment.

This includes device deficiencies that might have led to a serious adverse event if:

- 1) Suitable action had not been taken, or
- 2) Intervention had not been made, or
- 3) Circumstances had been less fortunate.

These are handled under the serious adverse event reporting.

Planned hospitalization for a pre-existing condition, or a procedure required by the CIP, without serious deterioration in health, is not considered a serious adverse event.

18.4.1. Serious adverse device effect (SADE)

A serious adverse device effect is an adverse device effect that has resulted in any of the consequences characteristic of a serious adverse event.

18.4.2. Anticipated serious adverse device effect (ASADE)

There are no ASADE.

18.4.3. Unanticipated serious adverse device effect (USADE)

An unanticipated serious adverse device effect is a serious adverse device effect which by its nature, incidence, severity or outcome has not been identified in the current version of the risk analysis report.

18.5. Medical care of subjects

Principal investigator shall ensure that adequate medical care is provided, during and after participation in the clinical investigation, to a subject experiencing an adverse event. All ongoing ADEs, SAEs, SADEs and DDs that could have led to a SAE at subject termination will be followed according to the Risk Benefit analysis (see 8.2). An ongoing adverse event at subject termination visit is documented as the current status for the adverse event and will not be followed up.

The subjects shall be informed of any new significant findings occurring during the clinical investigation, including the need for additional medical care that can be required, and of the nature and possible cause of any adverse events experienced.

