5.1. General

The study is a randomised, single-blinded controlled crossover study. The total study duration for the individual subject will be between 2 days – 14 days consisting of three site visits. Visits 0 and 1 can be performed on the same day, and it is possible to perform visit 1 and visit 2 on two consecutive days. For visit 1 and 2, catheterizations will be performed in a hospital setting by a health care professional for bladder emptying assessment and collection of urine samples for haematuria assessment.

A sub-group of subjects (all enrolled subjects at DK sites) will be asked to conduct a self-catheterization at visit 2 after HCP catheterization and evaluate discomfort and PVR.

(Figure 5-1) Randomized controlled crossover investigation with two products.

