5.3. Secondary endpoints

- Number of flow-stop episodes derived from a catheterisation profile (catheterisation performed by a healthcare professional), [number].
- Average residual volume post catheterisation (PVR) measured with a bladder scanner (triplicate measurements), [mL],
- Number of Adverse events, [number]

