- Pre-catheterization volume measured in triplicate with a bladder scanner. All measurements must be above 150 ml to proceed

- Catheterisation with 1st randomly assigned product (by HCP)
 - **NB!** HCP should count to 3 sec. if suspicious of a flow-stop before rotating the catheter to make it more clear on the profile.
- Catheterization profile (urine volume + number of flow stops)
- Volume at 1st flow stop and post catheterization volume noted from scale
- Number of flow stops noted
- Catheter used for catheterization (including size), position, and time for start of catheterization is noted
- Residual volume (PVR) (bladder scanner) (three measurements)
- Post-catheterisation dipstick test for haematuria, leukocyturia and Specific gravity
- Scheduling Visit (V2), after Baseline Visit (V1) (within visit window)
- Complete eCRF

Visit 2 (V2):

NB! Ask for change in relevant medical history since last visit. The subject should not have changed their medication the last 24 hours before V2 or show symptoms of UTI (assessed by investigator). If signs of UTI, they must be rescheduled and registration of AE. The position used for the HCP catheterisation must be the same as the position at visit 1.

- Review of Adverse events/Serious adverse events/Adverse device events, Device deficiencies and Protocol Deviations
- Review of changes in concomitant medication
- Information regarding menstrual cycle
- Pre-catheterization volume measured in triplicate with a bladder scanner. All measurements must be above 150 ml to proceed
- Catheterisation with 2nd randomly assigned product (by HCP)
 - **NB!** HCP should count to 3 sec. if suspicious of a flow-stop before rotating the catheter to make it more clear on the profile.
- Catheterization profile (urine volume + number of flow stops)
- Volume at 1st flow stop and post catheterization volume noted from scale
- Number of flow stops noted
- Catheter used for catheterization (including size), position, and time for start of catheterization is noted
- Residual volume (PVR) (bladder scanner) (three measurements)
- Post-catheterisation dipstick test for haematuria, leukocyturia and Specific gravity.
- DK only: Subjects will be asked to perform an additional self-catheterization at site after fluid intake
 - Pre self-catheterization volume measured in triplicate with a bladder scanner. All three measurements must be above 150 ml to proceed.
 - Post self-catheterization measure residual volume with triplicate bladder scan.

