7.3. Flow-chart

Table 1 chart showing the connection between visits and assessments.

Visit(V)	V0	V1	V2
Timing of visit (Weeks)	0	0	1-7 days after V1
Activity			
Introduction to investigation and review of Subject Information Form/Informed Consent Form	X		
Signed Informed Consent		X	
Allocation of subject number		X	
Check of in- and exclusion criteria	X	X	
Pregnancy test (urine dipstick) – for subjects of childbearing potential only		X	
Baseline information		X	
Information regarding menstrual cycle		X	X
Perform device accountability		X	X
Catheterisation by HCP		X	X
Bladder scan before and after catheterization		X	X
Recording of catheterization profile (data box)		X	X
Urine volume at 1 st flow stop (scale)		X	X

Number of flow-stop episodes counted by HCP	X	X
Urine volume post catheterization (scale)	X	X
Position, catheterisation start time and catheter registered	X	X
Post catheterisation dipstick for haematuria, leukocytes, and specific gravity	X	X
Self-catheterisation (DK only)		X
TriPLICATE bladder scan before to ensure minimum 150ml		X
Position and catheter registered		X
TriPLICATE bladder scan after to measure residual volume		X
Subject to complete discomfort on VAS		X
Assessment of subject's wellbeing and compliance with CIP	X	X
Concomitant medication potentially affecting urinary function (assessed by investigator) and pain management	X	X
AEs/ADEs/SAEs/SADEs	X	X
Device deficiencies	X	X
Protocol deviations	X	X
Complete eCRF	X	X
Termination form		X

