8.1. Risk-benefit analysis of the investigational device

A risk management process has been performed in accordance with the requirements stated in ISO 14971:2019 and in accordance with internal Coloplast procedures, including design verification, validated test methods, risk analysis and completion of a biological evaluation report for the investigational device.

Risks have been proven minimized or eliminated through appropriate risk control measures, confirmed by pre-clinical bench, laboratory, and biological safety evaluations.

The following risks will be mitigated by actions during the clinical investigation.

- Urinary tract infection. The subject is instructed to contact the investigator/designee, if the subject experience any symptoms or signs of a new UTI.
- Mild pain or bleeding. If discovered, this must be discussed with the investigator/designee.

To mitigate and reduce the risks, the investigator/designees will be trained, according to the IFU, in use of the device.

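### Adverse-event follow-up is scheduled for 1 to 7 days after the period-1 catheter but only for the rest of Visit 2 after the period-2 catheter, so by-device counts understate delayed events

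*Combined protocol and SAP*

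**What the plan says.** - **Endpoint and reporting.** Section 5.3 lists "Number of Adverse events, [number" among the secondary endpoints, and Section 3.1 ties the safety objective to CE marking. Section 10.1 (statistical design) presents summaries by device. Section 10.5 says AEs will be listed or summarised, and gives no denominator and no split by period.
- **Schedule.** Section 5.1: "The total study duration for the individual subject will be between 2 days – 14 days consisting of three site visits". In the Section 7.3 flow-chart, Visit 2 falls "1-7 days after V1". The row "AEs/ADEs/SAEs/SADEs" is marked at Visits 1 and 2, the row "Termination form" is marked at Visit 2, and there is no column after Visit 2.
- **Order of events at Visit 2.** Section 7.2 lists "Review of Adverse events/Serious adverse events/Adverse device events, Device deficiencies and Protocol Deviations" near the start, before the second catheterisation by the health care professional. After it come the scans, the dipstick, the Danish self-catheterisation with discomfort scores, termination and eCRF completion. No second AE review is listed.
- **Passive routes.** Section 8.1: "Urinary tract infection. The subject is instructed to contact the investigator/designee, if the subject experience any symptoms or signs of a new UTI". Section 7.2 provides a form for unscheduled calls or visits. Section 18.6.1 sets 24-hour reporting for serious events and device effects from the time the site learns of them. None of these is tied to a period after termination.
- **Events ongoing at termination.** Section 18.5 first says that ongoing device effects, serious events and certain device deficiencies are followed. It then says: "An ongoing adverse event at subject termination visit is documented as the current status for the adverse event and will not be followed up".

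**The concern.** Each subject has one catheterisation by a health care professional with each device, but the two uses are not observed alike. The first is followed until Visit 2, where staff ask about AEs and check for symptoms of urinary tract infection (UTI). The second is followed only until the subject leaves. A new event after that enters the database only if the subject or the site raises it. No section says when AE collection ends.

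The AE count is a listed endpoint serving the safety objective, and UTI is both a named risk (Section 8.1) and an anticipated device effect (Section 18.2). If each device's count is read as coming from 72 equally observed uses, the incidence of delayed events is understated and the reassurance from a low or zero count is overstated.

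**Working it through.** The plan states no figure on this point, so there is none to reproduce. The check sets out observation per use and then sizes the loss.

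**Inputs**
- Subjects: 72 (Sections 4.6 and 10.6).
- Two sequences, randomised in blocks of 8 (Section 5.7), so each device comes second in about half of the subjects.
- Observation after the period-1 use: 1 to 7 days (Section 7.3).
- Scheduled observation after the period-2 use: the rest of Visit 2, somewhat longer at Danish sites because of the added self-catheterisation.
- Rate p of delayed events per use: the documents give only verbal categories (Section 18.2), so p = 0.5%, 1%, 2% and 5% are assumptions.

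**Step 1: uses followed per device.** 72 / 2 = 36 period-1 uses with follow-up and 36 period-2 uses with essentially none.

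**Step 2: observation time per device.** Now: 36 × 1 = 36 to 36 × 7 = 252 subject-days. With a matching window after Visit 2: 72 × 1 = 72 to 72 × 7 = 504 subject-days.

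**Step 3: chance of seeing at least one delayed event per device.** P = 1 − (1 − p)^n, and the expected count is n × p. For example, at p = 1%, 1 − 0.99^36 = 30.4% and 1 − 0.99^72 = 51.5%.

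| Assumed p | Expected, n = 36 | P, n = 36 | Expected, n = 72 | P, n = 72 |
|---|---|---|---|---|
| 0.5% | 0.18 | 16.5% | 0.36 | 30.3% |
| 1% | 0.36 | 30.4% | 0.72 | 51.5% |
| 2% | 0.72 | 51.7% | 1.44 | 76.7% |
| 5% | 1.80 | 84.2% | 3.60 | 97.5% |

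**Step 4: what zero events would rule out.** The exact one-sided 95% upper limit is 1 − 0.05^(1/n).
- n = 36: 1 − 0.05^(1/36) = 8.0%.
- n = 72: 1 − 0.05^(1/72) = 4.1%.
- With the 60 subjects on which Section 10.6 bases its power, n = 30 gives 9.5% and n = 60 gives 4.9%.

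**Step 5: effect on the device comparison.** If both devices lose follow-up in about half of their uses, expected delayed-event counts fall from 72p to 36p for each. The ratio (36 × p1) / (36 × p2) = p1 / p2 is unchanged. The loss is in absolute counts and precision.

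Steps 3 and 4 treat every period-1 use as fully followed. Where Visit 2 is the day after Visit 1, that is generous to the plan.

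**The case against.** The case against is substantial.

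- **New events are not shut out.** A reader might infer that delayed events after the second catheter are never seen. The documents do not support that: the passive routes in Sections 7.2, 8.1 and 18.6.1 carry no end date. What is missing is active ascertainment and a stated end of collection.
- **The Section 18.5 sentence is weak evidence.** It concerns events already ongoing, and the sentence before it keeps device-related and serious events under follow-up. The gap is shown by the flow-chart and the Visit 2 list.
- **Much of the expected harm is immediate.** Stinging and pain are described as occurring during catheterisation, and haematuria is tested by dipstick at both visits. The 1 to 3 days in Section 8.2 is a healing time, so it does not show that micro-trauma first appears after the visit. UTI is the clearest delayed risk, and Section 18.2 rates it very unlikely. At 0.5% to 1%, fewer than one event per device is expected even from 72 uses.
- **No AE comparison is tested.** Superiority rests on the primary endpoint alone (pass/fail criteria, Section 10).
- **Attribution is poor.** Subjects self-catheterise at least three times daily, and Section 4.6 allots one study catheter of each type per subject. A UTI some days later follows many non-study uses.

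These points limit the size of the concern but do not remove it. The attribution problem applies equally to the Visit 1 to Visit 2 window, which the plan already treats as worth reviewing. The rarity of delayed events makes doubling the followed uses more useful, since a zero count is then the likely result to be interpreted.

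**Conclusion.** The point holds as an inequality of scheduled ascertainment between periods, together with an unstated end of AE collection. About 36 of 72 uses of each device have 1 to 7 days closed by an active review, and about 36 have only the rest of the visit. Pooled by device, the counts understate delayed events. A zero count supports an upper limit of about 8.0% rather than the 4.1% that 72 followed uses would give.

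A reader might go further and infer a built-in bias between devices. The randomised order does not support that: the gap falls on both devices alike.

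The result assumes near-equal sequences, full capture in the period-1 window, and little passive reporting after Visit 2. The detection probabilities also rest on assumed rates. The primary endpoint and the superiority claim are unaffected. This is a low-cost improvement to a listed safety endpoint.

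**What to change.** 1. Add one telephone AE query after Visit 2, with a window matching that between Visit 1 and Visit 2, and complete the termination form after it. The existing unscheduled-call form could be adapted. Add the contact to Sections 7.2 and 7.3.
2. State in the protocol when AE collection ends.
3. Reconcile the two adjacent rules in Section 18.5 on events ongoing at termination, so that sites know which events each covers.
4. If no call is added, amend Section 10.5. Tabulate AEs by device and period, separate events with onset at the visit from later ones, and base delayed-event incidence on period-1 uses only (about 36 per device).

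The first item costs about 72 short calls, a small protocol change and up to a week more per subject. Late events will remain hard to attribute, because subjects also use their own catheters. The other items cost only wording.
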